4.3 Magnetic Resonance Imaging

Magnetic Resonance Imaging (MRI) will be used as a noninvasive assessment tool to obtain quantitative measures to assess progress in graft maturity and rehabilitation towards safe return to sport. As the injured ACL undergoes ligamentization, MRI will be used to monitor the progress of each participant through T2* analysis and volume at the following time intervals: 3months, 6months, 9months, 12months, 18months, and 24months. MRIs will review the integrity of each graft, placement within the tunnel, and tunnel healing, and healing of the donor site (30).

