2.2 Primary Effectiveness Endpoint

FTA results as well as measurements from MRI evaluation will be recorded and utilized to quantify the healing and ACL graft maturation processes. MRI evaluation will be performed in accordance with accepted ACL imaging protocols. This data will then be compared to FTA results and MRI evaluation from patients who did not undergo the bioaugmentation technique for ACL reconstruction.

3 Hypotheses

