3.2 Alternative Hypothesis

H_1 – Participants undergoing the proposed bioaugmentation technique for ACL reconstruction will have improved healing times and graft maturation as evidenced by functional assessment scores and MRI evaluation when compared to matched participants who only underwent ACL reconstruction without bioaugmentation.

A Randomized, Single Blinded Study of the Augmentation of Anterior Cruciate Ligament Reconstruction using Stump-Derived Mesenchymal Stem Cells Versus Standard of Care Anterior Cruciate Ligament Reconstruction

4 Study Design and Procedures

Study design will be a prospective, single-blinded, randomized, single-center trial. Patients at the Andrews Institute who meet the inclusion criteria will have the study explained in detail and informed consent will be obtained as outlined below. Fifty patients will be blinded, randomized, and undergo an ACL reconstruction surgery. Twenty-Five randomized patients will receive standard of care (SOC) ACL reconstruction surgery. Twenty-Five randomized patients will receive ACL reconstruction surgery augmented with the patient's ACL stump tissue harvested with the GraftNet device (Arthrex, Naples, FL).

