4.1 Intraoperative Tissue Harvest and Application

A tissue sample will be harvested from each participant with the GraftNet device (one per surgery) during ACL reconstruction from the ACL stump. During the intra-articular preparation phase of the reconstruction, the tissue sample collected from the ACL stump will be applied to the ACL graft on the back table during the graft preparation phase.

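### Graft volume feeds the primary MRI assessment, but implanted graft size is not recorded and the tissue applied in the augmented arm may itself add volume

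*Protocol*

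**What the plan says.** Section 2.2 (Primary Effectiveness Endpoint) says that, besides the functional test results, "measurements from MRI evaluation will be recorded and utilized to quantify the healing and ACL graft maturation processes". These are then "compared to FTA results and MRI evaluation from patients who did not undergo the bioaugmentation technique for ACL reconstruction". Section 2.2 does not name the MRI variables. Section 4.3 does: MRI is to "obtain quantitative measures to assess progress in graft maturity and rehabilitation towards safe return to sport", and progress is monitored "through T2* analysis and volume at the following time intervals", namely 3, 6, 9, 12, 18 and 24 months. T2* and volume are the two quantitative measures named. Section 4.2 places no MRI at visit one, so the first scan is at 3 months.

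On treatment, Section 4 states "Twenty-Five randomized patients will receive standard of care (SOC) ACL reconstruction surgery", and the other 25 receive reconstruction augmented with their own stump tissue. Section 4.1 says that this tissue "will be applied to the ACL graft on the back table during the graft preparation phase", that is, before implantation. The same section describes the harvest as done in every participant and does not restrict the application to one arm.

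The protocol does not list graft type, prepared diameter, prepared length or the amount of tissue applied as data to be recorded. It does not say whether a larger or a smaller volume indicates maturation.

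**The concern.** Volume at 3 months or later is the size of the graft that went in plus whatever has happened since. Only the second part bears on maturation. Two separate things obscure it.

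- **Implanted size.** Grafts differ between patients. Randomization balances this on average, so it does not bias the comparison. With 25 per arm, however, it inflates the variance and leaves room for a chance imbalance that nobody could see or adjust for.
- **Added tissue.** The intervention puts material on the object whose volume is measured. If some of it persists, the arms differ in volume without any difference in healing. Randomization does not remove this, because it is a consequence of the assigned treatment.

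Because the protocol states no direction, either a larger or a smaller augmented graft could be called better maturation after the data are seen.

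The collection of graft size is a matter for the protocol. A statistical analysis plan can adjust only for what was measured, and size before implantation must be captured in the operating room.

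**Working it through.** The protocol gives no alpha, power, SD or effect size, so it has no figure of its own to reproduce. What follows is illustration.

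**Input from the protocol:** 25 per arm (Section 4).

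**Assumptions:** two-sided 5% two-sample t-test; 80% power; correlation r between implanted size and later MRI volume of 0.5 to 0.7; one-arm bulk artefact b of 0.1 to 0.5 SD of volume; no true effect on healing when false-positive rates are computed.

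**1. Noise from implanted size.** The standard error of the chance difference in mean implanted size is √(2/25) = 0.283 SD. By the normal approximation, the probability of an imbalance beyond 0.25 SD in either direction is 2 × [1 − Φ(0.25/0.283)] = 38%. Beyond 0.5 SD it is 8%. To show scale with assumed diameters: treating the graft as a cylinder of fixed length, 9 mm instead of 8 mm gives (9/8)² = 1.27, or 27% more volume.

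**2. Gain from adjustment.** The unadjusted detectable effect is 0.809 SD. A covariate with correlation r multiplies the residual SD by √(1 − r²), ignoring the one degree of freedom lost.
- r = 0.5: 0.809 × 0.866 = 0.70 SD (25% of the variance removed).
- r = 0.7: 0.809 × 0.714 = 0.58 SD (49% removed).

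**3. False positives from added bulk, unadjusted.** This is the rejection probability of the t-test at a true difference of b:

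| Artefact b (SD) | False-positive rate |
|---|---|
| 0.1 | 6% |
| 0.2 | 11% |
| 0.3 | 18% |
| 0.5 | 41% |

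**4. What adjustment for size before application does to the artefact.** That covariate cannot contain the added tissue, so the adjusted difference keeps all of b while the residual SD shrinks. For b = 0.3:
- r = 0.5: 0.3/0.866 = 0.346 residual SD, false-positive rate about 22%.
- r = 0.7: 0.3/0.714 = 0.420 residual SD, about 31%.

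The covariate therefore helps with the first problem and, used alone, makes the second somewhat worse (18% becomes 22–31%).

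**5. Change from the 3-month scan.** This would cancel stable implanted size and any bulk that stays constant. It would not cancel bulk that is resorbed between scans. It would also subtract any real effect already present at 3 months, because that scan is taken after treatment.

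**The case against.** The strongest reply is that the obvious remedy does not touch the more serious problem. Size measured before tissue is applied is a precision covariate, and step 4 shows that it sharpens the test around an artefact it leaves intact. This stands, and the fix has to go beyond that covariate.

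Second, nothing in the protocol gives the amount of tissue applied, how much of it is still measurable at 3 months, or the SD of volume. At 0.1 SD the false-positive rate is 6%, hardly above nominal. This also stands. A reader might infer that a volume difference in this trial would be an artefact, but the protocol supports only that it could be.

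Third, covariates and the direction of benefit are often left to a statistical analysis plan, which may exist, and Section 4.3 can be read as within-patient monitoring. This is fair as regards the analysis. It does not answer the missing measurement. Routine operative notes may contain graft size, but the protocol does not call for it.

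Fourth, one might infer that T2* should replace volume as the maturation measure. The protocol ranks neither, and nothing in it shows that T2* is unaffected by tissue applied to the graft.

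Finally, the one-arm premise rests on Section 4. Section 4.1, read alone, describes tissue harvested from all participants and applied to the graft. The premise holds only if Section 4 governs.

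**Conclusion.** The point holds in a limited form. Volume is one of two quantitative MRI measures behind the primary endpoint, it is first seen at 3 months, and the protocol provides for no record of the implanted size it started from. The resulting loss of precision is avoidable: a detectable effect of 0.81 SD could be 0.70–0.58 SD with the same 50 patients, if the correlation is 0.5–0.7.

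It would be too strong to say that natural variation in graft size biases the comparison, since randomization balances it in expectation. It would also be too strong to put a size on the bulk artefact. The 6% to 41% range only shows how the error rate would move if the artefact were 0.1 to 0.5 SD. A between-arm volume difference, as now planned, cannot by itself be attributed to maturation.

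The change should be made, because intraoperative size cannot be recovered later unless it happens to be in the operative notes.

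**What to change.** - In both arms, record graft type and prepared diameter and length on the back table before any tissue is applied. Use this size as a covariate in the volume comparison.
- In the augmented arm, also record the graft size again after application, or the amount of tissue applied. Report this beside the volume result. It is a consequence of assignment, so it should not simply be added as another covariate.
- State in advance which direction of volume counts as maturation.
- Do not interpret a between-arm volume difference as maturation on its own. Report it together with T2* and the recorded added volume.
- Reconcile Section 4 (tissue in 25 patients) with Section 4.1 (harvest in every participant). Section 8.5 also mentions a bovine collagen matrix that Section 4.1 does not describe. Whether it is used, and in which arm, should be clarified, since it could add volume too.

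The cost is a few fields on the surgical form, one covariate and a sentence on direction. The downside is that volume carries less weight as evidence of maturation. No extra MRI, visit or patient is needed.

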4.4 Functional Testing Algorithm

Using the Davies Functional Algorithm (29), the following tests will be performed: Basic Measurements, Sensorimotor System Testing: Balance/Proprioceptive Testing, Closed Kinetic Chain Testing, Open Kinetic Chain Testing, Functional Jump Tests, Functional Hop Tests, Lower Extremity Functional Tests, and Sport-Specific/Position-Specific Testing. Each test will be performed incrementally, and participants will not advance to the next series of tests until the prior assessment has been completed at a satisfactory level. The participants' results from the Functional Testing Algorithm (FTA) and the time required to complete the progression during the rehabilitation period will be quantified and analyzed according to demographic data and pre-injury activity level. The participants will be stratified according to activity level. Participant groups will include general orthopedic patients, recreational athletes, and competitive athletes and will be tested by the FTA accordingly.

5 Patient Reported Outcome Measures (PROMs)

Patient reported outcome measures will be used to quantify physical and psychological aspects of rehabilitation after ACL reconstruction monthly after informed consent has been obtained and surgery has occurred. The patient reported outcomes can be collected in paper format or through the REDCap system. The patient reported outcomes will follow the presented follow up visit schedule: 3months, 6months, 9months, 12months, 18months, and 24months.

A Randomized, Single Blinded Study of the Augmentation of Anterior Cruciate Ligament Reconstruction using Stump-Derived Mesenchymal Stem Cells Versus Standard of Care Anterior Cruciate Ligament Reconstruction

5.1 Tampa Kinesiophobia Scale (TKS):

The fear of reinjury can be a barrier to the rehabilitation of competitive athletes after ACL reconstruction. To quantify the fear associated with reinjury, the Tampa Kinesiophobia (TSK) scale will be provided monthly to participants in the study (31). Kinesiophobia is defined as the fear of movement (31). This measure will be collected to evaluate progression in rehabilitation to take into account not only the physical health of the injured athlete but also the psychological effects and rehabilitation.

5.2 International Knee Documentation Committee Subjective Knee Evaluation Form (IKDC):

The International Knee Documentation Committee Subjective Knee Evaluation (IKDC) form will contribute to the comprehensive data set to evaluate each participant's confidence in performance on a monthly schedule. IKDC has 19 questions that will take approximately 3-5 minutes for each participant to complete monthly. IKDC data will be collected by the AREF research team and reviewed with the primary investigator.

5.3 Patient Reported Outcomes Measurements Information Systems (PROMIS):

The patient reported outcomes measurement information system (PROMIS) is a measurement system used monthly in this project to assess monthly the overall health functioning and rehabilitation levels of each participant (32). AREF will collect this data and alert the primary investigator if any adverse outcomes are found. The addition of the PROMIS data is required to ensure that a comprehensive assessment of overall functioning is reviewed in the determination of athlete readiness to return to sport.

5.4 Single Assessment Numeric Evaluation (SANE):

The SANE assessment is a single question patient reported outcome from a rating of 0-100 for each participant to score their current functioning in comparison to their pre-injury functioning level (33). This assessment will be collected monthly after ACL reconstruction by the AREF research team for each participant.

6 Participant Recruitment

A total of 50 participants will be recruited through the Andrews Institute physician practices. A recruitment flyer will be posted within the physicians' offices, on social media platforms and posted in community locations. Potential participants will be prescreened for inclusion and exclusion criteria through standard of care medical evaluations. Participants meeting the

A Randomized, Single Blinded Study of the Augmentation of Anterior Cruciate Ligament Reconstruction using Stump-Derived Mesenchymal Stem Cells Versus Standard of Care Anterior Cruciate Ligament Reconstruction

inclusion criteria will have the study explained to them by one of the members of the research team, and they will be given an opportunity to participate if they are interested. Once a potential participant has agreed to be involved in the study, they will go through the described informed consent process.

6.1 Screening Process

Once interested patients are identified and prescreened, a screening visit (visit 1) will be scheduled. During the screening visit, a screening form will be completed which includes the inclusion and exclusion criterion below. If an individual answers "yes" to any of the initial screening exclusion questions, they will be informed that they do not qualify for the study, and they will be informed that they can keep their screening form and their medical care will not be adversely affected by not enrolling in the study. If all answers are "no" then the form will be placed in the study documents and the enrollment process will continue.

Once the screening requirements are met, the informed consent form will be provided to the participant or electronically via REDCap for review ensure the volunteer understands the details of the study including the benefits and risk factors. The patient will be provided sufficient time to consent and sign the informed consent form (ICF). The principal investigator (PI) and study/research team will be available to answer any questions or provide clarifications during the informed consent process.

6.2 Participant Eligibility

6.2.1 Inclusion Criteria:

Patients between the ages of 14 and 50 who are scheduled to have ACL reconstruction by one of the investigating physicians will be pre-screened for participation in this study.

6.2.2 Exclusion criteria:

Exclusion criteria will include patients requiring ACL and posterior cruciate ligament (PCL) combined surgery, patients with a history of an autoimmune disease, diabetes, a blood/clotting disorder, or history of previous surgery on the injured knee. Patients will undergo informed consent and an unidentifiable patient study number will be created.

6.3 Benefits

Direct benefit to the intervention group participant may include improved outcome following the ACL reconstruction and earlier return to baseline functioning level. Indirect benefits to the

A Randomized, Single Blinded Study of the Augmentation of Anterior Cruciate Ligament Reconstruction using Stump-Derived Mesenchymal Stem Cells Versus Standard of Care Anterior Cruciate Ligament Reconstruction

participant include increased surgical follow-up, and additional post-surgery monitoring. This study may also help direct clinical practice in developing preferred techniques to augment orthopedic surgical procedures (aspirational benefit).

6.4 Compensation

Compensation will not be provided to participants in this study.

7 Informed Consent 21 CFR 50

In adherence to the 21 CFR 50, Protection of Human Subjects Guidelines, the informed consent process will be performed by one of the study investigators or staff, in the research office on paper or electronically via REDCap. REDCap is a secure web application for building and managing online surveys and databases. While REDCap can be used to collect virtually any type of data in any environment (including compliance with 21 CFR Part 11, FISMA, HIPAA, and GDPR), it is specifically geared to support online and offline data capture for research studies and operations. The REDCap Consortium, a vast support network of collaborators, is composed of thousands of active institutional partners in over one hundred countries who utilize and support their own individual REDCap systems. All participants will have the study described to them and will give as much time as they require to read an approved, stamped version of the informed consent document. After physical or electronic signing of the informed consent document, participants will be given a copy for their records. This process will take place only after the patient has consented to proceed with the study.

7.1 Consent Withdrawal:

During the informed consent procedure, participants will be informed that if at any point during the study, consent may be withdrawn. To withdraw consent, participants can request in writing to withdraw HIPAA authorization and the research site will not use or provide any health information to researchers. At this time, the link between the participant's health information will be severed with the research team. This process for consent withdrawal will be reviewed with each participant and identified barriers will be addressed at the time of informed consent.

8 Review of Safety

8.1 Adverse Event (AE)

An adverse event is any untoward or unfavorable medical occurrence in the human subject, including any abnormal sign, symptom, or disease, temporally associated with

A Randomized, Single Blinded Study of the Augmentation of Anterior Cruciate Ligament Reconstruction using Stump-Derived Mesenchymal Stem Cells Versus Standard of Care Anterior Cruciate Ligament Reconstruction

the subject's participation in the research, whether considered related to the subject's participation in the research.

8.2 Serious Adverse Event (SAE)

Serious adverse events are any events that:

- Result in death
- Is life threatening, or places the participant at immediate risk of death from the event as it occurred
- Requires or prolongs hospitalization
- Causes persistent or significant disability or incapacity
- Results in congenital anomalies or birth defects
- Is another condition which investigators just to represent significant hazards

8.3 Unanticipated Problem (UP)

Defined by DHHS 45 CFR part 46 as any incident, experience, or outcome that meets the following criteria.

- Unexpected, in terms of nature, severity, or frequency, given (a) the research procedures that are described in the protocol-related documents, such as the IRB-approved research protocol and informed consent document; and (b) the characteristics of the study population.
- Related or possibly related to participation in the research (in this guidance document, possibly related means there is a reasonable possibility that the incident, experience, or outcome may have been caused by the procedures involved in the research);
- Suggests that the research places participants or others at a greater risk of harm (including physical, psychological, economic, or social harm) than was previously known or recognized.

A Randomized, Single Blinded Study of the Augmentation of Anterior Cruciate Ligament Reconstruction using Stump-Derived Mesenchymal Stem Cells Versus Standard of Care Anterior Cruciate Ligament Reconstruction

8.4 AE & SAE Collection and Reporting

Throughout the study the research team will monitor the occurrence of AE and SAE. Data will be collected if an instance occurs, and the PI will be notified. All AE data, such as onset date, resolution date, outcome and treatments given will be documented in the source documents and will be recorded in the electronic data capture system (EDC) and analyzed for severity to follow reporting protocol if severity level.

Follow-up will occur using the provided safety monitoring form if AE occurs. The follow up will end either when the symptoms resolve or up to 30 days past the end of the study participation.

8.5 Expected Risks and Discomforts

Risks and Discomforts: As with any research involving human subjects there is the inherent risk of a breach in patient confidentiality. This will be minimized using participant code numbers and adhering to all HIPAA guidelines. Standard sterile precautions for surgical procedures will be utilized for all ACL surgeries. With any surgery there remains the risk of infection, bleeding, and swelling. The collection of soft tissue samples with the GraftNet device does not increase the risk associated with the surgical procedure. MSC transplantation has been deemed safe by the Food and Drug Administration (FDA) (34). However, as with all stem cell therapy, there is the inherent risk of tumorigenicity (35) (36). Long-term follow up is needed to further elucidate these risks. Use of the bovine collagen matrix presents minimal risk to the participant. Other studies utilizing this implant did not report any discomforts or adverse events attributed to the collagen matrix implant (23).

9 Data Management Procedures

All personal information is strictly confidential, and no names will be disclosed except as required by law. All information and data collected including patient reported outcomes measures during this research will be compiled into an Excel spreadsheet. This spreadsheet will not contain protected health information. The spreadsheet will be stored in a secure password protected folder on a laptop that only the study investigators will have access to and will be permanently deleted following publication of all manuscripts, if any, written as a result of this research. Records related to this study will be securely retained in a secure location for a period of 3 years after the completion of the study or longer as required by law. At that time, all records will be properly destroyed.

A Randomized, Single Blinded Study of the Augmentation of Anterior Cruciate Ligament Reconstruction using Stump-Derived Mesenchymal Stem Cells Versus Standard of Care Anterior Cruciate Ligament Reconstruction

10 Data Analysis

Data will be compiled in Microsoft Excel and REDCap. All compiled data will be de-identified.

11 Statistical Considerations

Statistical analysis will be performed in excel and SAS Studio (Version 3.8 on SAS 9.4, SAS Institute Inc., Cary, NC). Descriptive statistics will be compiled for all numeral measures (outcomes).

12 Quality Control and Assurance

